6.5.1 Provision of avelumab or pembrolizumab

Avelumab will be given as standard of care and will be billed to the study participant's insurance.

Since the initial writing of this protocol, the PD-1 inhibitor pembrolizumab has been FDA approved for the treatment of metastatic Merkel cell carcinoma. For patients with a history of infusion reactions to avelumab, pembrolizumab can be administered with this study in place of avelumab at 200 mg every 3 weeks or at any subsequent FDA approved dosing regimen for this indication, starting 14 days following investigational T cell infusion.

6.5.2 Avelumab or pembrolizumab infusion

Avelumab will be administered as standard of care. Currently, the FDA recommended dosing is 10 mg/kg over the duration of 1 hour (-10/+70 minutes) at an interval of once every 2 weeks.

Premedications suggested by package label include pretreatment with H1 blockers (diphenhydramine 12.5mg to 50 mg PO or IV, or equivalent) and acetaminophen PO 500 to 650 mg for first several doses.

First avelumab dose is intended 14 +/- 3 days after first T cell infusion up to 50 weeks (total of 25 infusions) or longer, as clinically indicated under the standard of care or until Off Study Criteria are met as described in **Section 10**. The first dose of avelumab will be calculated based on the actual weight of the participant determined at study entry. As avelumab is being administered as standard of care, if alternate doses or schedules are approved by the FDA for avelumab for treatment of advanced MCC (for instance q4 week dosing or flat instead of weight-based dosing), these doses and schedules may be substituted at the discretion of the investigator and treating oncologist. Following first avelumab infusion, participants will be observed for 1 hour post infusion for potential infusion-related reactions. Participants will receive avelumab once every 2 weeks for 50 weeks or until the criteria in **Section 11.7** (Off Study Criteria) are met. Modifications of the infusion rate due to infusion-related reactions and management of acute infusion reactions are below as recommended in product label.

The first avelumab infusion after each T cell infusion should be administered at Fred Hutch for monitoring in case of acute adverse event. Subsequent infusions may be given locally by a licensed oncology professional experienced in prescribing immunotherapy. A “Dear Physician” letter detailing the study treatment and providing contact information to the study team including emergency contact information will be provided to local/non-Fred Hutch oncologists.

Monitoring exams and blood work associated with avelumab infusion will be performed clinically at the discretion of the treating oncologist and in keeping with institutional standards for avelumab infusion.

If pembrolizumab is given instead of avelumab, it will be administered over 30 minutes intravenously with similar monitoring as above and without premedications unless at the direction of the clinical team.

Typical practice at Fred Hutch: A physical exam is usually performed by an APP or MD within 48 hours of infusion and blood work is obtained. Typically, this blood work typically includes a CBC with differential, basic metabolic panel, liver function panel, and LDH with each infusion, and a serum cortisol, TSH, free T4, amylase, and lipase with every other infusion. Cortisol, TSH, free T4, amylase and lipase do not often result prior to that day’s infusion, however these are followed longitudinally to determine whether there is a need for hormone replacement. However, different institutions have different standards and policies for avelumab or pembrolizumab monitoring, and labs may need to be more or less often for safety reasons or include additional labs depending on patient’s course, therefore the protocol will allow flexibility in the avelumab or pembrolizumab.

Avelumab or pembrolizumab doses may be held, rescheduled or dosages reduced at the discretion of treating oncologist in keeping with standard clinical practice. If immune related adverse event secondary to avelumab or pembrolizumab suspected or confirmed, treating oncologist to discuss management with study team and joint management decision established.

6.5.3 Recommended Supportive Care, Additional Treatment, and Monitoring

Prophylactic treatment/measures are recommended for patients at risk for tumor lysis syndrome (TLS) according to institutional or clinical standards. Supportive care for the management of TLS is detailed in **Section 7**.

The use of red blood cells and platelet transfusions, and/or colony-stimulating factors is permitted according to institutional or clinical standards.

The use of prophylactic or empiric anti-infective agents (e.g., trimethoprim/sulfamethoxazole for pneumocystis pneumonia [PCP] prophylaxis, broad spectrum antibiotics, antifungals, or antiviral agents for febrile neutropenia) is permitted according to institutional standards.

Hospitalization may be required after study treatment to manage treatment-associated toxicities.

7. POTENTIAL RISKS AND TOXICITY MONITORING

7.1 Toxicity associated with interferon gamma administration

Administration of interferon gamma can commonly cause fever, headache, chills, fatigue, rash, nausea and vomiting, diarrhea, myalgia, abdominal pain, depression, arthralgias, and local injection site reactions. More rare but serious adverse events include colitis, hypersensitivity reactions, elevations in liver function tests, myocardial infarction, cytopenias, hypokalemia, stevens johnson syndrome and neurologic effects.

7.2 Management of toxicity associated with interferon gamma

Patients will be premedicated with acetaminophen 650 mg prior to each dose.

Mild acute administration reactions should be managed with antipyretics, antihistamines, and anti-emetics as clinically appropriate, and these may be added to prophylaxis for future doses.

Corticosteroids should be avoided. Appropriate emergency medications (e.g., epinephrine, diphenhydramine, etc.) should be readily available during administration and institutional guidelines should be followed for the treatment of anaphylaxis.

Fever and flu like symptoms should be treated with antipyretics as needed.

Local reactions can be managed by choosing alternate sites.

Severe symptoms or those involving hypoxemia or hypotension, particularly following T cell infusion, should be treated as presumptive cytokine release syndrome and treated as below.

Doses may be held or treatment discontinued due to intolerable side effects or grade III or higher adverse events attributable to interferon gamma. Adverse events attributable to T cell infusion (e.g. cytokine release syndrome) will be assumed to be synergistic with interferon gamma, and interferon gamma will be held in these cases.

7.3 Acute Toxicity Associated with T-Cell Infusion (Infusion reaction)

Administration of MCPyV-specific TCRs may cause infusion reactions, including fever, rigors, rash, urticaria, dyspnea, hypotension, and/or nausea. Mild infusion reactions should be managed with antipyretics, antihistamines, and anti-emetics as clinically appropriate. Corticosteroids should be avoided. Appropriate emergency medications (e.g., epinephrine, diphenhydramine, etc.) should be readily available during administration and institutional guidelines should be followed for the treatment of anaphylaxis.

7.4 Management of Acute Infusion Reaction(s)

For infusion reactions or any clinically significant changes from baseline, stop administration of MCPyV-specific TCRs, notify the provider to have the patient assessed and administer appropriate symptomatic treatment.

- Fever, chills, and temperature elevations $> 38.0^{\circ}\text{C}$ may be managed with acetaminophen 650 mg PO every 4 to 6 hrs. All patients who develop fever $> 38.0^{\circ}\text{C}$ or chills should have a blood culture drawn and the PI or designee should be notified.
- Nausea and/or vomiting may be managed with ondansetron 8 mg po or other antiemetics (excluding corticosteroids).
- Hypotension should be managed initially by fluid administration.
- Hypoxemia should be managed initially with supplemental oxygen.

After the resolution of symptoms, an order may be obtained to resume administration at a reduced rate. If symptoms re-occur, stop the administration, administer symptomatic treatment as ordered and contact the IMTX attending for the final determination to discontinue the infusion.

If an adverse reaction occurred during the IEC infusion or post-monitoring period, the provider will determine in collaboration with the research team if any workup is needed.

Patients requiring discontinuation of the infusion may be eligible for re-treatment if the cause is deemed not related to the infusion.

7.5 Acute Toxicity Associated with Avelumab or Pembrolizumab Infusion

As with all monoclonal antibody therapies, avelumab or pembrolizumab carries a risk of allergic reaction, although infusion reactions are more common with avelumab¹⁰ (20%) than pembrolizumab⁷⁸ (2%) in MCC. If hypersensitivity reaction occurs, the participant must be treated according to the best available medical practice. Hypersensitivity reactions associated temporally with infusion of pembrolizumab or avelumab will be attributed to pembrolizumab or avelumab. Reactions not temporally linked with pembrolizumab or avelumab will be attributed to interferon gamma.

Avelumab: special precautions

As infusion reactions have been commonly observed with avelumab, pre-treatment with H1 blockers (diphenhydramine 12.5-50 mg PO, IV, or equivalent), and acetaminophen (500 to 650 mg orally) will be administered 30 to 60 minutes prior to the first avelumab infusion to mitigate infusion-related reactions including hypersensitivity reactions. Pretreatment for subsequent infusions or pembrolizumab infusions will be per treating physician/institutional standard of care.

Infusion of avelumab or pembrolizumab will be stopped in case of Grade ≥ 3 hypersensitivity, inflammatory response, or infusion-related reaction. The treatment recommendations for infusion-related reactions, severe hypersensitivity reactions, and tumor lysis syndrome are as outlined below. These may be substituted with an institution's specific guideline/standard practice for avelumab infusion related reactions.

Avelumab or pembrolizumab: Infusion-related reactions

Symptoms
Fever
Chills
Rigors
Diaphoresis
Headache

Management

Table 6. Treatment modification for symptoms of infusion-related reactions caused by Avelumab or Pembrolizumab

NCI-CTCAE Grade	Treatment Modification for Avelumab
Grade 1 – mild Mild transient reaction; infusion interruption not indicated; intervention not indicated.	Decrease the Avelumab or Pembrolizumab infusion rate by 50% and monitor closely for any worsening. The total infusion time for Avelumab or Pembrolizumab should not exceed 120 minutes.
Grade 2 – moderate Therapy or infusion interruption indicated but responds promptly to symptomatic treatment (for example, antihistamines, NSAIDs, narcotics, IV fluids); prophylactic medications indicated for \leq 24 hours.	Stop Avelumab or Pembrolizumab infusion. Resume infusion at 50% of previous rate once infusion-related reaction has resolved or decreased in severity to $<$ Grade 1 and monitor closely for any worsening.
Grade 3 or Grade 4 – severe or life-threatening Grade 3: Prolonged (for example, not rapidly responsive to symptomatic medication and/or brief interruption of infusion); recurrence of symptoms following initial improvement; hospitalization indicated for clinical sequelae. Grade 4: Life-threatening consequences; urgent intervention indicated.	Stop the avelumab or pembrolizumab infusion immediately and disconnect infusion tubing from the participant. Participants who have a reaction associated with avelumab may not receive any further administration of avelumab as part of this study, but they may receive administration of pembrolizumab as part of this study. Participants who have a reaction associated with pembrolizumab may not receive any further administration of pembrolizumab as part of this study. In addition, they may not receive any administration of avelumab as part of this study.”

Definitions: IV=intravenous, NCI-CTCAE=National Cancer Institute-Common Terminology Criteria for Adverse Event, NSAIDs=nonsteroidal anti-inflammatory drugs,

Once the avelumab or pembrolizumab infusion rate has been decreased by 50% or interrupted due to an infusion-related reaction, it must remain decreased for all subsequent infusions. If the participant has a second infusion-related reaction of Grade \geq 2 on the slower infusion rate, the infusion should be stopped, and the participant should be removed from avelumab or pembrolizumab treatment. If a participant experiences a Grade 3 or 4 infusion-related reaction at any time, the participant must discontinue avelumab or pembrolizumab. Patients who experience infusions reactions with avelumab may receive pembrolizumab for future infusions. Patients who experience infusion reactions with pembrolizumab may not receive avelumab for future infusions.

Management of severe hypersensitivity reactions and flu-like symptoms due to avelumab or pembrolizumab infusions

If hypersensitivity reaction occurs, the participant must be treated according to the best available medical practice. Participants should be instructed to report any delayed reactions to the Investigator immediately.

Symptoms of severe hypersensitivity reaction

Impaired airway

Decreased oxygen saturation (< 92%)

Confusion

Lethargy

Hypotension

Pale / clammy skin

Cyanosis

Management

Epinephrine injection and dexamethasone infusion

Patient should be placed on monitor immediately

Alert ICU for possible transfer if required

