Title of Study: ATTAC-MCC: Phase I/II study of Autologous CD8+ and CD4+ Transgenic T cells expressing high affinity MCPyV-specific TCRs combined with Avelumab and Class I MHC - upregulation in patients with metastatic MCC refractory to PD-1 axis blockade		
Sponsor: Fred Hutch		Phase of Development: I/II
Study Objectives: Primary: Safety, Efficacy Secondary/Exploratory: T cell persistence, T cell phenotype, T cell function, T cell localization into tumor, epitope spreading of T cell responses, recurrence-free survival, overall survival		
Study Purpose and Rationale: 
Metastatic Merkel cell carcinoma is an aggressive skin cancer caused by a virus. There are currently no effective treatments for individuals whose cancer progresses on or after treatment with PD-1 axis immunotherapies. We have developed an engineered autologous T cell therapy targeting Merkel cell polyomavirus. In a phase I/II trial, we seek to determine the safety and potential efficacy of this T cell therapy combined with interferon gamma, in addition to standard treatments (anti-PDL1/avelumab) for patients whose virus-associated metastatic/unresectable MCC tumors are resistant to PD-1 axis treatments.
		
Study Population: 
Individuals that are HLA-A02+ with metastatic Merkel cell polyomavirus associated Merkel cell carcinoma whose disease has progressed on or after treatment with a PD-1 axis checkpoint inhibitor
		
Test Product: 
 - FH-MCVA2TCR: Autologous CD8+ and CD4+ T cells transduced with transgenic TCR A2-MCC1. - Interferon gamma 		
Additional Interventions (not test product, given as standard of care): 
 - Avelumab - Pembrolizumab (as an alternative to avelumab) 		
Safety Assessments: Ongoing; with evaluation of part I/II transition after three patients have been treated		
DLT Definition: 
DLTs will be assessed for 28 days following the infusion of the TCR transgenic T cell product. The following events will be considered DLTs if they are attributed as at least possibly related to TCR T
		

cell administration. Grading will be done in accordance with NCI CTCAE version 5.0 unless otherwise specified.

1. Grade 3 allergic reaction or other event that leads to discontinuation of TCR T cell infusion
2. Grade 3 autoimmune reactions
3. Grade 3 neurotoxicity that does not resolve to grade 1 or less within 7 days
4. Grade 3 CRS that does not resolve to < grade 3 within 7 days.

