12.4 Attribution of Adverse Event

Association or relatedness to the study agent will be assessed by the PI as follows:

Definite (must have all 4)	
 • Has a reasonable temporal relationship to the intervention
---------------------------------------	--

	
 • Could not have readily been produced by the patient's clinical state or have been due to environmental or other interventions • Follows a known pattern of response to intervention • Disappears or decreases with reduction in dose or cessation of intervention and recurs with re-exposure
Probable (must have 3)	
 • Has a reasonable temporal relationship to the intervention • Could not have readily been produced by the patient's clinical state or have been due to environmental or other interventions • Follows a known pattern of response to intervention • Disappears or decreases with reduction in dose or cessation of intervention
Possible (must have 2)	
 • Has a reasonable temporal relationship to the intervention • Could not have readily been produced by the patient's clinical state • Could not readily have been due to environmental or other interventions • Follows a known pattern of response to intervention
Unlikely (must have 2)	
 • Does not have a temporal relationship to the intervention • Could readily have been produced by the patient's clinical state • Could have been due to environmental or other interventions • Does not follow a known pattern of response to intervention • Does not reappear or worsen with reintroduction of intervention

For general AE assessment, an AE is considered related if it is assessed as definitely, probably, or possibly related; unrelated if it is assessed as unlikely related or unrelated.

For determination of IND safety reporting, AE attribution will be assessed according to the suspected adverse reaction definition described in 21 CFR 312.32 as an AE for which there is a reasonable possibility that the drug caused the adverse event where “reasonable possibility” means there is evidence to suggest a causal relationship between the drug and the AE. The IND Sponsor will report suspected adverse reactions that are both serious and unexpected to the FDA as an IND safety report, in accordance with regulations under 21 CFR 312.32.

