12.6 Expected Grade 3-4 Adverse Events

Avelumab, pembrolizumab, interferon gamma, and T cell infusions each have associated, expected, transient toxicities that will not be considered grounds for therapy discontinuation nor counted as adverse events for determination of treatment safety/dose limiting toxicity. These will however be appropriately logged and reported as with any other grade 3-4 toxicity below.

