12.6.2 Expected Adverse Events: Interferon gamma

Expected toxicities attributable to interferon gamma and considered exceptions to criteria for discontinuation include transient inflammatory responses (Fever, rash, flu like symptoms, **outlined in 7.1**) resulting in Grade 3 or 4 toxicities that return to baseline within 2 weeks.

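### Section 7.5 leaves T cells out as a cause of hypersensitivity, so read literally an allergic reaction during the first T-cell infusion may not count as a T-cell DLT

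*Combined protocol and SAP*

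**What the plan says.** **Attribution rule.** Section 7.5, under the avelumab/pembrolizumab heading, attributes hypersensitivity timed with the checkpoint inhibitor to that drug. It continues: "Reactions not temporally linked with pembrolizumab or avelumab will be attributed to interferon gamma".

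**DLT definition (synopsis).** The window is 28 days after T-cell infusion. The gate is: "The following events will be considered DLTs if they are attributed as at least possibly related to TCR T" cell administration. Criterion 1 is: "Grade 3 allergic reaction or other event that leads to discontinuation of TCR T cell infusion".

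**T cells as a cause.** Section 7.3: "Administration of MCPyV-specific TCRs may cause infusion reactions, including fever, rigors, rash, urticaria, dyspnea, hypotension, and/or nausea". It also refers to anaphylaxis treatment.

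**General attribution.** Section 12.4: "Association or relatedness to the study agent will be assessed by the PI as follows". Definite, probable and possible all count as related. Section 7.2 accepts shared causation: events attributed to the T cells "will be assumed to be synergistic with interferon gamma, and interferon gamma will be held in these cases".

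**What is counted.** The primary safety event (13.2.1) is grade 3 or higher toxicity at least possibly due to any study treatment, less the exceptions in 12.5 and 12.6. The part I rule (4.4, 13.2.2) suspends the trial if two or more of the first three patients have treatment-related grade 3-4 toxicity.

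**Exceptions.** Under 12.6, expected transient toxicities are not grounds for discontinuation, "nor counted as adverse events for determination of treatment safety/dose limiting toxicity". For interferon gamma, 12.6.2 covers transient inflammatory responses (fever, rash, flu-like symptoms, with a pointer to 7.1) "resulting in Grade 3 or 4 toxicities that return to baseline within 2 weeks".

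**The concern.** DLT criterion 1 exists to catch an allergic reaction to the T-cell product. It can do so only if T cells may be recorded as at least a possible cause, and the 7.5 default does not offer them. The plan thus has one rule that names the event as a T-cell DLT and another that, taken at its word, attributes it elsewhere.

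Attribution is used in four further places:

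- Section 4.4 has the DSMB consider the cell dose or construct where T cells were implicated.
- Section 6.4.4 makes interferon gamma in cycle 2 depend on whether a grade 3 or higher toxicity was attributed to it.
- Section 7.4 makes re-treatment after a discontinued infusion depend on the cause being judged unrelated to that infusion.
- Section 12.6.2 applies only to toxicity attributed to interferon gamma, so the label is the first step of a possible route out of the primary safety count.

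**Working it through.** **1. Which agents are present when the T cells go in (cycle 1).** Interferon gamma starts 5-7 days before the infusion and lasts 4 weeks (6.3). Avelumab is first given at day 14 +/- 3 (6.5.2), so not before day 14 - 3 = 11; pembrolizumab starts from day 14 (6.5.1). A reaction during the first T-cell infusion is therefore not timed with an on-study checkpoint inhibitor, and the 7.5 default applies.

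Two further cases show that the sentence does not work as a general rule:

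- Section 13.1 expects about 12 of 16 patients to receive a checkpoint inhibitor. For the other 16 - 12 = 4, every hypersensitivity event would go to interferon gamma.
- Section 6.4.4 allows a second T-cell infusion without interferon gamma. A reaction then, if not timed with a checkpoint inhibitor, would be attributed to a drug not given in that cycle.

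**2. The same reaction under each section.** Take a grade 3 reaction with urticaria and hypotension that stops the first T-cell infusion.

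| Section | Result |
|---|---|
| 7.5 | Interferon gamma; T cells not an option |
| 7.3 | A recognised T-cell infusion reaction |
| 12.4 | At least possibly related to T cells: two features suffice, and temporal relationship and known pattern (7.3) are both met |
| DLT criterion 1 | A DLT if 12.4 governs; not a DLT if 7.5 governs and attribution is exclusive |

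No passage ranks 7.5 against 12.4. Section 12.4 speaks of the study agent in the singular and does not say whether each agent is rated separately.

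**3. Which counts change.**

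| Count | Relabelled to interferon gamma only | Relabelled and also excepted under 12.6.2 |
|---|---|---|
| T-cell DLT | May be lost | Lost |
| Primary safety event (13.2.1) | Unchanged | Lost |
| Two-of-three rule (4.4, 13.2.2) | Unchanged | Lost, if 12.6 is applied there |

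Whether the last column can arise is not settled. Section 12.6.2 names fever, rash and flu-like symptoms and points to 7.1. Section 7.1 mentions hypersensitivity, but in a separate sentence among rarer, serious events.

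**4. Size if events were lost.** First the plan's own figures. The boundaries in 13.2.2 (2/2, 3/3-4, ..., 9/15-16) are the smallest counts whose one-sided 80% Clopper-Pearson lower limit exceeds 40%. An exact binomial recursion over 16 patients, checking the boundary after each one, gives suspension probabilities of 0.062 at 20% true toxicity and 0.847 at 60%. The plan states about 0.06 and 0.84 from simulation, so they reproduce.

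The documents do not give the share of patients with toxicity whose only counted event would be excepted. Let f be that share, assumed to be 10% to 30%. The counted rate is q = p(1 - f), and P(at least 2 of 3) = 3q²(1 - q) + q³. For example, with p = 0.60 and f = 0.10, q = 0.54, and 3 × 0.2916 × 0.46 + 0.1575 = 0.560.

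| True rate p | f | q | P(suspension), 13.2.2 boundaries | P(at least 2 of 3), part I |
|---|---|---|---|---|
| 0.60 | 0 | 0.60 | 0.847 | 0.648 |
| 0.60 | 0.10 | 0.54 | 0.726 | 0.560 |
| 0.60 | 0.20 | 0.48 | 0.578 | 0.470 |
| 0.60 | 0.30 | 0.42 | 0.425 | 0.381 |
| 0.50 | 0 | 0.50 | 0.629 | 0.500 |
| 0.50 | 0.10 | 0.45 | 0.501 | 0.425 |
| 0.50 | 0.20 | 0.40 | 0.377 | 0.352 |
| 0.50 | 0.30 | 0.35 | 0.267 | 0.282 |

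The f = 0 rows also describe relabelling without exception: the change is zero.

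**The case against.** The best defence is context. The sentence sits under the checkpoint-inhibitor heading, directly after 7.3 and 7.4 on T-cell infusion reactions. It can be read as separating two overlapping drugs, much as 7.11 does for gastrointestinal toxicity. The investigator could still rate a reaction as possibly related to T cells under 12.4. Section 7.4 expects a judgement on whether the cause was the T-cell infusion, and 7.2 shows that attribution need not be exclusive.

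There are also safeguards. Excepted events are still logged and reported (12.6). The DSMB reviews all grade 3 or greater toxicities and decides on the move to part II (14.2). For serious events the Medical Monitor assesses relationship separately, and either party's view suffices to classify an event as related (12.7.2).

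This stands against three stronger inferences that a reader might draw:

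- **That such a reaction cannot count as a T-cell DLT.** The documents contradict each other; they do not set a settled bar.
- **That every reaction before about day 11 is in fact reassigned.** That takes the literal reading of 7.5 as the governing one.
- **That one relabelled event turns two of three (suspend) into one of three (proceed).** Both counts include toxicity from any study treatment, so this also needs the 12.6.2 exception. The more natural reading of 12.6.2 leaves serious hypersensitivity outside it, though the pointer to 7.1 and the mention of rash leave doubt.

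The defence does not remove the conflict. The 7.5 sentence is unqualified and no text makes it yield to 12.4. The safeguards review events after classification; they do not say how to classify them.

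**Conclusion.** The point holds as a contradiction in the attribution rules. Followed literally, 7.5 sends an allergic reaction during the first T-cell infusion to interferon gamma and empties the allergic part of DLT criterion 1, against 7.3 and 12.4.

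The certain effect is confined to attribution: whether the event may be classed as a T-cell DLT, and what the cycle 2 interferon gamma provision (6.4.4) and the re-treatment provision (7.4) then read. The effect on the primary safety count and the part I rule is zero from relabelling alone. It becomes material only if 12.6.2 is also applied, which the text neither establishes nor excludes. The figures of 0.726 to 0.425 (against 0.847) are conditional on that reading and on an assumed 10% to 30% share; they are not an estimate of what will happen. In a trial with three-patient decisions and at most 16 patients, the classification of a single event should not depend on which section is consulted.

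**What to change.** Reconcile 7.5 with DLT criterion 1, 7.3 and 12.4:

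1. Limit the default sentence in 7.5 to telling checkpoint-inhibitor reactions apart from others, so that it no longer assigns the remainder to interferon gamma.
2. State that relatedness under 12.4 is recorded separately for T cells, interferon gamma and checkpoint inhibitor, and that more than one agent may be recorded.
3. State that the 12.6.2 exception does not remove from the DLT count or the primary safety count a hypersensitivity reaction assessed as at least possibly related to T cells.
4. Check that 6.4.4 and 7.4 say which recorded attribution they rely on. This asks only for consistency, not for a change in clinical management.

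The cost is a few sentences and, if the case report form holds a single relatedness item, one item per agent. The observed toxicity rate may be slightly less favourable. The stated operating characteristics in 13.2.2 do not change.
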